4.2.4 End of Treatment

An EOT visit should be performed as soon as possible after the decision to discontinue the study treatment, but preferably at least 30 days after last dose of study treatment unless a new anticancer treatment is planned to be administered before the 30 days, in which case EOT should be conducted before initiation of the new anticancer treatment.

When EOT coincides with a scheduled visit, the scheduled visit will become EOT.

4.2.5 Follow-up Period

All patients, regardless of disease status, will be followed every 12 weeks for up to 3 years from the EOT, or until withdrawal of consent, loss to follow-up, or death, whichever occurs first.

When disease assessments or blood draw are not planned for a follow-up visit, the visit can be done by phone.

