- [Section 6.8.4 Contraceptive Guidance](#): Added “If WOCBP use hormonal contraceptives such as birth control pills, a second barrier method of contraception (e.g., condoms) must be used during idelalisib treatment until 1 month after last dose of idelalisib.”
- [Section 8.2 Eliciting and Reporting Adverse Events/Serious Adverse Events](#): Amended to extend collection of SAEs to at least 76 days after the last dose of loncastuximab tesirine or until initiation of new anticancer treatment, whichever is earlier, to ensure appropriate surveillance of any late onset events while eliminating the confounding influence of other anti-cancer therapies based on updated conjugated loncastuximab tesirine Ab half-life (15.2 days). As idelalisib is a comparator, SAE follow-up duration for idelalisib was also updated to align with loncastuximab tesirine. [Table 1](#) and [Table 2](#) were updated to reflect the change.

In addition, non-substantial clarifications/corrections for inconsistencies, as well as administrative and editorial changes were included; revisions to the protocol text have also been applied to the synopsis section.

List of Prior Protocol Versions

Document	Version Date	Rationale for Changes
Protocol Amendment 2.0	19 Feb 2021	The primary reason for Protocol Amendment 2 was to extend the contraception duration post loncastuximab tesirine for female participants with childbearing potential from 6 to 9 months to align with current regulatory guidance.
Protocol Amendment 1.0	25 Nov 2020	The primary reason for Protocol Amendment 1 was to incorporate the changes in response to the US FDA feedback. This amendment combines changes regarding safety monitoring, study stratification, and statistical analysis. In addition, updates include removal of QTcF eligibility criteria and dexamethasone equivalent as premedication, assigning ORR as key secondary endpoint, as well as modifications on PRO schedules.
Protocol Original	26 Aug 2020	

[figure not shown]
Table of Contents

Summary of Changes for Protocol Amendment 3.0	4
List of Prior Protocol Versions.....	6
Table of Contents	7
List of Tables.....	11
List of Figures.....	11
List of Abbreviations.....	12
Protocol Synopsis.....	15
Schedule of Events.....	24
1 Introduction and Background	31
1.1 Disease Background.....	31
1.2 Description of the Study Drugs.....	32
1.2.1 Loncastuximab tesirine (ADCT-402).....	32
1.2.2 Idelalisib	33
1.2.3 Clinical Study Data for Loncastuximab Tesirine and Idelalisib.....	33

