Abbreviations: ADA: anti-drug antibody; AE: adverse events; BP: blood pressure; β -HCG: β subunit of Human chorionic gonadotropin; C: cycle; C1D1: cycle 1 day 1; [REDACTED] CMV: cytomegalovirus; CT: computerized tomography; ECG: electrocardiogram; ECOG: Eastern Cooperative Oncology Group; EOI: end of infusion; EOT: end of treatment; FACT-Lym: The Functional Assessment of Cancer Treatment-Lymphoma questionnaire; FDG: (18)F-fluorodeoxyglucose; [REDACTED]; HBV: hepatitis B virus; HCV: hepatitis C virus; HIV: human immunodeficiency virus; HR: heart rate; ICF: informed consent form; IV: Intravenous; MRI: Magnetic resonance imaging; PCR: polymerase chain reaction; PK: pharmacokinetics; PRO-CTCAE: Patient-Reported Outcomes Version of the Common Terminology Criteria for Adverse Events; RR: respiratory rate; SAE: serious AEs; Temp: temperature;.

Visit Scheduling Windows:

- Treatment Period: Visit day \pm 3 days (excluding C1D1 which is the reference day).
- EOT: As soon as possible after decision to discontinue the study treatment but preferably at least 30 days after last dose of study treatment unless a new anticancer treatment is planned to be administered before the 30 days, in which case EOT should be conducted before initiation of the new anticancer treatment.
- Follow-up Period: Visit day \pm 14 days.

²Vitals should be taken at pre-dose and EOI for every loncastuximab tesirine dosing visit.

³Positron-emission tomography-computed tomography will be used to perform imaging study. If disease is not FDG-avid at baseline, CT or MRI may be used. Screening imaging must be performed within 4 weeks prior to C1D1 and the same assessment method must be used throughout the study. Week 6 and Week 12 imaging should be performed within \pm 5 days of the scheduled timepoint. All other imaging for disease assessment should be performed within \pm 2 weeks of the

scheduled time point. Imaging for disease assessment should be performed at the scheduled timepoint even if drug dosing is delayed. Additional disease assessments may be obtained, if clinically indicated.

⁴During follow-up period disease assessments to be performed in patients who discontinued study treatment for reasons other than disease progression or initiation of other anti-cancer therapy (except for hematopoietic stem cell transplant).

⁵ \leq 3days prior to administration of study treatment for loncastuximab tesirine arm patients.

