8.2 Eliciting and Reporting Adverse Events/Serious Adverse Events

Patients will be instructed to contact the Investigator at any time after ICF signature if any symptoms develop. At each study visit, patients will be asked a nonleading question to elicit any medically related changes in their well-being. Patients may also report AEs voluntarily and they will be instructed to contact the Investigator between visits if any symptoms develop or worsen.

AEs will be reported starting when the patient provides written informed consent. Clinically significant medical conditions present at the time of ICF signature will be reported as medical history. Clinically significant medical conditions that start or worsen after ICF signature will be reported as AEs.

All AEs, regardless of relationship to study treatment, will be reported from the time the patient signs the ICF until 30 days after the last dose of study treatment.

All SAEs, regardless of relationship to study treatment, will be reported from the date patient signs the ICF until at least 76 days after last dose of study drug, or start of new anticancer therapy, whichever is earlier; thereafter, only related SAEs will be reported.

Whenever possible, AEs should be reported as a diagnosis rather than individual signs and symptoms. If no diagnosis is available or has been identified, then the primary symptom is reported.

In general, the term ‘disease progression’ should not be used for reporting an AE/SAE. However, AEs/SAEs that are complications of disease progression should be reported.

All AEs reported or observed during the study will be recorded on the AE page of the eCRF. Information to be collected will include event term, date of onset, assessment of severity (Section 8.3), seriousness (Section 8.1), relationship to study treatment (Section 8.4), action taken with study treatment, date of resolution of the event or ongoing (when no resolution by the end of the reporting period), any required treatment or evaluations, and outcome.

New SAEs and any recurrent episodes, progression, or complications of the original SAE must be reported to the pharmacovigilance department of the Sponsor or delegate (e.g., contract

research organization [CRO]) within 24 hours after the time site personnel first learn about the event. Reporting will occur through the EDC system.

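### Safety collection is counted from last dose but follow-up visits from end of treatment, so the first follow-up visit nearly always falls after day 76, and an early end-of-treatment visit leaves unequal parts of the 30-day adverse-event window unvisited in the two arms

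*Combined protocol and SAP*

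**What the plan says.** Section 8.2 counts both safety windows from last dose. AEs "will be reported from the time the patient signs the ICF until 30 days after the last dose of study treatment". The limit for all SAEs is "until at least 76 days after last dose of study drug, or start of new anticancer therapy, whichever is earlier". Beyond that point the duty narrows to SAEs judged related. The Summary of Changes for Amendment 3.0 derives the 76 days from a conjugated-antibody half-life of 15.2 days. It gives surveillance of late-onset events as the purpose, and says the idelalisib period was set to match.

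The visits that serve these windows are counted differently. Section 4.2.5: "All patients, regardless of disease status, will be followed every 12 weeks for up to 3 years from the EOT". Tables 1 and 2 give follow-up visits a window of ±14 days. Section 4.2.4 times EOT "as soon as possible after the decision to discontinue the study treatment, but preferably at least 30 days after last dose", allows it sooner if new anticancer treatment is planned, and adds: "When EOT coincides with a scheduled visit, the scheduled visit will become EOT". It states no minimum interval from last dose for that last rule.

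Under Section 8.2, AEs are elicited by an open question at each study visit, and patients are told to get in touch between visits. Tables 1 and 2 schedule no routine laboratory tests or physical examination in follow-up, and neither ties a contact to day 30 or day 76 after last dose.

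**The concern.** A reporting window works best when a scheduled contact closes it. Here the windows and the contacts have different origins, so the delay between an event and the first time a patient is asked about it depends on when EOT happened to fall.

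Two things are at stake. First, an SAE after EOT that the patient does not volunteer may be elicited only by recall, weeks after the window has closed. The 24-hour reporting clock starts when site staff learn of the event, and the Section 4.3 pausing rules count reported events, so delay in learning of an event can delay both. Second, the definition of a treatment-emergent AE in Section 9.8.1 uses the same 30-day limit. If the visited part of those 30 days differs by arm, the main safety tables compare unequally observed periods. Safety matters more than usual here: Sections 2.1 and 9.1 say that the sample size was set to give safety data on about 100 patients treated with loncastuximab tesirine.

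**Working it through.** **The plan's own figure.** 5 × 15.2 = 76.0 days, as stated. On a simple half-life calculation, 0.5^(30/15.2) = 0.255, so about a quarter of conjugated antibody remains at day 30. This applies to the loncastuximab tesirine arm only.

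**First follow-up visit.** Inputs: 12 weeks = 84 days from EOT (Section 4.2.5) and ±14 days (Tables 1 and 2). Day after last dose = EOT day + 84 ± 14.

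| EOT (days after last dose) | First follow-up visit | Allowed range | Days from EOT to day 76 |
|---|---|---|---|
| 30 | 114 | 100-128 | 46 |
| 21 | 105 | 91-119 | 55 |
| 0 | 84 | 70-98 | 76 |

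The nominal date is always after day 76. The earliest allowed date is EOT day + 70, which is 76 or less only if EOT is on day 6 or earlier. With EOT on day 0, 7 of the 29 allowed days (70 to 76) fall by day 76. A visit on day 70 would still leave the last days of the window until the next 12-week contact.

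Example: after EOT on day 30, an SAE on day 40 is first asked about at a follow-up visit 100 − 40 = 60 to 128 − 40 = 88 days later.

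**AE window left after an early EOT.** Unvisited days = 30 − EOT day.

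- Loncastuximab tesirine is given once per 21-day cycle (Section 4.2.3). With no dose delay, the next Day 1 visit is 21 days after last dose, or 18-24 with the ±3-day window. If it becomes EOT, 30 − 21 = 9 days remain (6-12).
- Idelalisib is taken twice daily throughout its 28-day cycle. If it is taken up to the visit, that visit is 0-1 day after last dose. If it becomes EOT, 29-30 days remain.
- If EOT is on day 30 or later, no days remain in either arm.

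**Imaging as an alternative contact.** Scans are counted from Cycle 1 Day 1, every 12 weeks to 2 years and then every 6 months. They continue after EOT in patients who stopped without progression or new therapy (Section 7.3; footnote 4 of Tables 1 and 2). Assume that EOT falls at a random point in the 84-day scan cycle. The chance of a scan date between EOT and day 76 is then (76 − EOT day)/84:

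- EOT day 30: 46/84 = 55%.
- EOT day 21: 55/84 = 65%.
- With 6-monthly scans (182 days): 46/182 = 25% and 55/182 = 30%.

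These figures apply only to patients still being scanned. The documents do not give that share. If it is f, the overall chance at EOT day 30 in the first 2 years is 0.55 × f: about 14% at f = 0.25 and 55% at f = 1.

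**The case against.** A reader might infer that the 76-day window closes with no scheduled contact of any kind. The documents do not support that. Patients who stopped without progression or new therapy go on being scanned, Section 7.3 pairs imaging with a clinical examination for lymphoma, and just over half or more of those still scanned in the first 2 years would have a scan date in the window. Patients who start new therapy have their window closed at that point, so those who keep the full 76 days overlap with those still scanned. This stands and narrows the point. It does not remove it: scan dates are not tied to last dose, imaging does not continue for patients who stopped for progression, and nothing says that an imaging attendance is a visit at which the AE question is asked.

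A reader might also infer that late events are lost. They are not. Patients may report at any time, and an event inside the window stays reportable when elicited later. Grade 4 and 5 events often reach the site without a routine visit. No figure in the documents shows how many SAEs would depend on recall.

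Finally, the arm difference is conditional. Section 4.2.4 prefers EOT at day 30 or later, and its rule on coinciding visits may be meant only to avoid duplicates. Idelalisib may also have been withheld before the visit, and a loncastuximab tesirine hold of more than 3 weeks (Table 4) puts EOT well past day 21. The difference therefore cannot be called systematic. It remains something that the text permits.

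**Conclusion.** The mismatch of origins is real. As written, the first follow-up visit comes after day 76 unless EOT is on days 0-6 and the visit is early. At the preferred EOT on day 30, it comes 24 to 52 days after the window closes (100 − 76 and 128 − 76). The consequence is delayed elicitation for patients not seen at a scan or by their own report; the reporting period itself is not cut short. When a scheduled Day 1 visit becomes EOT before day 30, about 9 days (6-12) of the AE window go unvisited in the loncastuximab tesirine arm and 29-30 in the idelalisib arm, so ascertainment of treatment-emergent AEs can differ by arm. That comparison assumes no dose delay and idelalisib taken up to the visit. How often EOT falls early, and what share of patients is still scanned, cannot be determined from the documents. The point is worth correcting because safety data drive the sample size and the correction is cheap.

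**What to change.** Reconcile Sections 4.2.4, 4.2.5 and 8.2 with Tables 1 and 2, so that safety contacts are counted from last dose in both arms.

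1. If EOT occurs before day 30, add a telephone AE contact at day 30 after last dose.
2. Time the first follow-up contact from last dose, on or shortly after day 76 (for example day 76-98), with AE and SAE elicitation marked in the tables. Telephone is enough where no scan or blood draw is due; Section 4.2.5 already allows this. The contact is not needed if EOT or another AE-eliciting visit already falls on or after day 76, as it may after a long dose hold, or if new anticancer therapy has closed the window.
3. State whether an imaging attendance counts as a visit at which AEs are elicited.

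In the day-40 example, the delay falls from 60-88 days to 36-58 (76 − 40 and 98 − 40). The change closes the 76-day window promptly but adds no contact between days 30 and 76, so some recall delay remains. The cost is protocol wording, one existing contact moved, and at most one extra telephone call for patients whose EOT is before day 30.

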4.2.6 End of Study

The end of study (EOS) occurs at the last scheduled visit/procedure for the last patient, unless the study is terminated earlier by Sponsor. The death date will be considered as the EOS date for an individual patient whose survival status was informed at any later contact date.

4.3 Study Stopping Rules

Once at least 15 patients have been treated with idelalisib, study enrollment will be paused for safety evaluation if any of the following occur:

1. The number of patients with reported Grade 5 toxicity in the loncastuximab tesirine arm is more than twice the number of patients with reported Grade 5 toxicity in the idelalisib arm.
2. Grade 4 skin toxicity is reported in >2 patients treated with loncastuximab tesirine and the incidence of Grade 4 skin toxicity in patients treated with loncastuximab tesirine is >5% and the incidence is at least 50% higher than the incidence in patients treated with idelalisib.
3. Grade 4 toxicity of edema or effusion is reported in >2 patients treated with loncastuximab tesirine and the incidence of Grade 4 toxicity of edema or effusion in patients treated with loncastuximab tesirine is >5% and at least 50% higher than the incidence in patients treated with idelalisib.

Safety evaluation will be performed by ADCT.

5 Patient Population

Patients must meet all inclusion criteria and none of the exclusion criteria to be eligible for the study. All criteria have to be assessed during Screening, unless otherwise specified.

Prospective approval of protocol deviations to recruitment and enrollment criteria, also known as protocol waivers or exemptions, is not permitted.

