4.1 Overview

This is a prospective, randomized, 2-arm, multi-center, and open-label Phase 2 study in patients with R/R FL. The study will enroll approximately 150 patients. Eligible patients will be randomly assigned to treatment with loncastuximab tesirine or idelalisib in a 2:1 ratio. A block randomization with stratification based on time since last systemic therapy (≤ 2 years vs >2 years) will be used. A non-binding futility analysis on the primary endpoint of CRR will be performed for the first 60 patients around 12 weeks after the 60th patient is randomized (enough time for 2 disease assessments). The duration of the study participation for each patient is defined as the time from the date of signed written informed consent to the completion of the follow-up period, withdrawal of consent, loss to follow-up, or death, whichever occurs first.

The study will include a screening period (up to 28 days), a treatment period (cycles of 3 weeks for loncastuximab tesirine treatment and cycles of 4 weeks for idelalisib treatment), and a follow-up period (approximately every 12 weeks visits) for up to 3 years from treatment discontinuation ([Section 4.2](#), study periods).

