4.2.2 Randomization

Patients who are eligible will be randomized via Interactive Response Technology (see Interactive Response Technology manual for details). The randomization will be stratified based on time since last systemic therapy (≤ 2 years vs >2 years). Block randomization with size of 3 will be used to generate the randomization list. Approximately 150 patients will be randomized (2:1 ratio) to receive either loncastuximab tesirine or idelalisib. For details on randomization steps and for treatment assignment, see [Section 6.3](#).

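### Does stopping rule 1, which compares Grade 5 counts with no minimum number of events, need rewriting because chance alone can trigger it?

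*Combined protocol and SAP*

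**What the plan says.** Section 4.3 (Study Stopping Rules) opens: "Once at least 15 patients have been treated with idelalisib, study enrollment will be paused for safety evaluation if any of the following occur". Three triggers follow.

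- Rule 1: "The number of patients with reported Grade 5 toxicity in the loncastuximab tesirine arm is more than twice the number of patients" with Grade 5 toxicity in the idelalisib arm. It sets no minimum count, no incidence floor and no margin.
- Rule 2 begins "Grade 4 skin toxicity is reported in >2 patients treated with loncastuximab tesirine and the incidence of Grade 4 skin toxicity" and adds two conditions: an incidence above 5% on loncastuximab tesirine, and that "the incidence is at least 50% higher than the incidence in patients treated with idelalisib".
- Rule 3 begins "Grade 4 toxicity of edema or effusion is reported in >2 patients treated with loncastuximab tesirine" and carries the same two further conditions.

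The section closes: "Safety evaluation will be performed by ADCT". It gives no look schedule, no expected Grade 5 rate and no operating characteristics. Section 4.2.2 states: "Approximately 150 patients will be randomized (2:1 ratio) to receive either loncastuximab tesirine or idelalisib". Table 7 in section 8.3 defines Grade 5 as death related to an adverse event, so rule 1 concerns fatal toxicity and not deaths from all causes.

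**The concern.** Rule 1 reads like a doubling threshold, but under 2:1 allocation it is not one. With twice as many patients on loncastuximab tesirine, equal risk already yields about twice as many events there. More than twice the count therefore means any excess in incidence, however small. With no minimum count, the first Grade 5 event in the trial can meet the rule, and under equal risk that event falls on loncastuximab tesirine two times in three.

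The neighbouring rules require more than 2 patients, an incidence above 5% and a 50% relative excess. Rule 1 has none of these guards, and the protocol does not say why. If the rule often fires by chance, enrollment could be held up without cause, and a pause would say little about whether the drug is harmful.

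**Working it through.** **Inputs.** Allocation 2:1 and about 150 patients, so 100 v 50 (sections 4.1 and 4.2.2). Permuted blocks of 3 (section 4.2.2). Rules active from 15 idelalisib-treated patients, hence about 30 on loncastuximab tesirine (section 4.3). The Grade 5 rate and the look schedule are assumptions, because the documents give neither: rates of 0.25% to 10%, checked after each patient.

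**The plan's own figures.** No operating characteristic is stated for the stopping rules, so there is none to reproduce. The 100 v 50 arm sizes can be checked against Tables 8 and 9. Exact Fisher power with 0.025 in one tail gives 99.9 / 96.1 / 87.3% for CRR (stated 99 / 96.1 / 87.3) and 84.1 / 67.3 / 41.7% for ORR (stated the same).

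**What rule 1 tests.** Let L and I be the Grade 5 counts, with n_L = 2·n_I patients treated. L > 2·I is then the same as L/n_L > I/n_I. The factor of two is the allocation ratio, so unequal arm size is already allowed for.

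**Hand check, single look at 30 v 15, 1% in both arms.** P(I = 0) = 0.99^15 = 0.860. P(L ≥ 1) = 1 − 0.99^30 = 0.260. The product is 0.224. The remaining terms (I = 1 with L ≥ 3, and so on) are negligible, and the exact total is 22%. At 100 v 50 the exact single-look figures are 41% at a 1% rate, 45% at 2% and 46% at 5%.

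**Hand check, continuous checking, 1%.** P(at least one event in 150) = 1 − 0.99^150 = 0.779. If the first event decides, 0.779 × 2/3 = 0.519, close to the simulated 51%.

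**Chance pauses under equal risk** (simulation, 40,000 trials per setting; probability of at least one pause):

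| Grade 5 rate, both arms | Rule 1 | As incidence only | Rule 1 with >2 patients | Form of rules 2 and 3 |
|---|---|---|---|---|
| 0.5% | 35% | 35% | 1% | 0.4% |
| 1% | 51% | 54% | 8% | 2% |
| 2% | 63% | 70% | 27% | 12% |
| 3% | 68% | 76% | 46% | 27% |
| 5% | 70% | 79% | 63% | 50% |
| 10% | 74% | 80% | 73% | 61% |

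At 0.25%, rule 1 gives 21%. If events lag enrollment by up to 10 or 25 blocks, rule 1 gives 29–33% at 0.5%, 45–50% at 1%, 61–63% at 2% and 72–74% at 5%.

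**Pauses when the risk on loncastuximab tesirine is tripled:**

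| Loncastuximab v idelalisib | Rule 1 | Rule 1 with >2 patients | Form of rules 2 and 3 |
|---|---|---|---|
| 3% v 1% | 86% | 57% | 32% |
| 6% v 2% | 95% | 90% | 78% |
| 9% v 3% | 97% | 97% | 93% |

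**Reading the tables.** Counting events as incidence gains nothing. Only a minimum count or a margin lowers the chance-pause rate. At 3% v 1%, a minimum of more than 2 patients raises the share of trials with no pause from 14% (100 − 86) to 43% (100 − 57); the form of rules 2 and 3 raises it to 68% (100 − 32).

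**The case for a change.** The strongest case for a change is that a minimum count is cheap and works well at low rates. At a common rate of 1%, 93% of first triggers are exactly 1 v 0. Requiring more than 2 patients cuts chance pauses from 51% to 8%, and it widens the gap between detection and chance pauses at 3% v 1%: 57 − 8 = 49 points, against 86 − 51 = 35 for rule 1. Rule 1 also fires in 31% (0.5% v 1%) to 45% (2.5% v 5%) of trials in which loncastuximab tesirine carries half the idelalisib risk. The pause is mandatory, section 4.3 gives no criterion for resuming, and deaths are reported as SAEs within 24 hours in any case (sections 8.1.2 and 8.2).

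Much of this stands. A pause under rule 1 is weak evidence of harm, and the protocol does not say that the sensitivity is deliberate. What does not follow is that the rule is wrong. The gap in points weighs a needless pause and a missed excess of fatal toxicity equally, and a safety group need not do so. SAE reporting does not in itself hold enrollment while the arms are compared. The difference from rules 2 and 3 is not a contradiction: those concern specified Grade 4 events, and rule 1 concerns fatal ones. The advantage of their form also shrinks as rates rise (70% v 50% at a 5% rate, 74% v 61% at 10%). The figures count trials with at least one pause; the number and length of pauses, and so the delay to enrollment, have not been computed.

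**Conclusion.** No change to the plan is needed; this is a fair trade-off. Rule 1 is highly sensitive, and under equal risk it would pause about 35% to 74% of trials at rates of 0.5% to 10% if checked after every patient. That range depends on rates and a look schedule the documents do not supply. Below about 1%, or at any single look, the figure is under half.

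Each available revision either fails or has a real cost. Restating the rule as incidence raises chance pauses (51% to 54% at 1%, 63% to 70% at 2%). A minimum count lowers them but lets more true excesses pass without a pause, most of all at low event rates. The missing look schedule and operating characteristics are details that the sponsor's safety group can settle in running the rule.

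Because the consequence is a pause for evaluation and not termination, and the events are fatal toxicities, accepting frequent chance pauses for higher detection is reasonable. Other statisticians might choose a minimum count, but the present rule is not an error.

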8.3 Assessment of Severity

The AEs will be graded according to CTCAE v5.0. For events not included in the CTCAE criteria, the severity of the AE is graded on a scale of 1 to 5 as shown in [Table 7](#).

Table 7. Definition of Severity Grades for CTCAE

Grade	Definition
1	Mild; asymptomatic or mild symptoms; clinical or diagnostic observations only; intervention not indicated.
2	Moderate; minimal, local or noninvasive intervention indicated; limiting age-appropriate instrumental activities of daily living (ADL). ^a
3	Severe or medically significant but not immediately life threatening; hospitalization or prolongation of hospitalization indicated; disabling; limiting self-care ADL. ^b
4	Life-threatening consequences; urgent intervention indicated.
5	Death related to adverse event.

^a ADL refers to preparing meals, shopping for groceries or clothes, using the telephone, managing money, etc.

^b Self-care ADL refers to bathing, dressing and undressing, feeding self, using the toilet, taking medications, and not bedridden.

The AEs characterized as intermittent do not require documentation of onset and duration of each episode.

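### Does safety stopping rule 1 need a stated resume and re-trigger condition because it can be met at one Grade 5 event against none?

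*Combined protocol and SAP*

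**What the plan says.** Section 4.3 of the protocol sets three rules behind one condition: "Once at least 15 patients have been treated with idelalisib, study enrollment will be paused for safety evaluation if any of the following occur".

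- **Rule 1** compares counts of patients. It is met when the number with Grade 5 toxicity "in the loncastuximab tesirine arm is more than twice the number of patients with reported Grade 5 toxicity in the idelalisib arm". It has no minimum count and no incidence threshold.
- **Rules 2 and 3** (skin toxicity; edema or effusion) have both. Rule 2 starts with "Grade 4 skin toxicity is reported in >2 patients treated with loncastuximab tesirine" and adds that the incidence "is >5% and the incidence is at least 50% higher than the incidence in patients treated with idelalisib". Rule 3 is built the same way.

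On what follows a trigger, the section has one sentence: "Safety evaluation will be performed by ADCT". It does not say when enrolment resumes, or what counts as a new trigger afterwards.

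Two other places bear on the count. Table 7 in section 8.3 defines Grade 5 as "Death related to adverse event". Section 8.2 collects all serious adverse events until at least 76 days after the last dose or the start of new anticancer therapy, whichever is earlier; "thereafter, only related SAEs will be reported".

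**The concern.** Rule 1 is the only one of the three about deaths, and it behaves unlike its neighbours. One loncastuximab tesirine death against none meets it, and enrolling event-free patients never undoes that. Rules 2 and 3 can lapse by dilution: 3/59 = 5.1% exceeds 5%, while 3/60 = 5.0% does not.

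The text allows three readings:

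- (a) the pause lasts as long as the inequality is true;
- (b) the rule acts only when the inequality becomes true, so a second pause requires it to clear and be met again;
- (c) each further loncastuximab tesirine Grade 5 event that leaves the inequality true is a new trigger.

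Under (a), enrolment stopped at 1 against 0 could restart only after an idelalisib death. Under (b), the rule could be used up early and say nothing at 2, 3 or 4 against 0, the pattern it should catch. It is also not spelled out whether Grade 5 toxicity means any such event or only one judged related to study drug. With a trigger at a single event, one classification could decide a pause.

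**Working it through.** **Inputs.** Rule 1 and the 15-patient condition come from section 4.3; 2:1 allocation in blocks of 3 and about 150 patients (100 and 50) from section 4.2.2. The documents give no Grade 5 rate and no operating characteristics for the rule, so there is no planned figure to reproduce. The per-patient risks below are assumptions.

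**Step 1: when the rule is met.** Let L and I be the cumulative numbers of patients with Grade 5 toxicity on loncastuximab tesirine and idelalisib. The rule is L > 2I. The smallest L that meets it is 1, 3, 5, 7 for I = 0, 1, 2, 3. Neither count can fall, so the inequality turns false only when I rises. From 1 against 0, one idelalisib event gives 1 against 1, which clears it; 3 against 1 meets it again.

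**Step 2: how often it fires with no true difference.** Exact recursion over 50 blocks of 3, events known at enrolment, rule active from 15 idelalisib patients:

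| Equal Grade 5 risk | Ever met | First met at exactly 1 vs 0, of those | Met a second time after clearing, of those |
|---|---|---|---|
| 1% | 51% | 92% | 2% |
| 2% | 63% | 76% | 9% |
| 3% | 68% | 59% | 16% |
| 5% | 71% | 32% | 26% |
| 8% | 73% | 11% | 35% |

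**Step 3: is the rule usually spent on the first event?** Only at low rates. When the rule becomes active, about 45 patients are in (30 and 15). The chance that none of them has a Grade 5 event is 0.99^45 = 64% at 1% risk but 0.95^45 = 10% at 5%. At the higher rates events have already accumulated, so the first trigger is usually at some other count. The share at 1 against 0 falls below one half just above 3.5%. If events are reported with a delay (mean 15 enrolments), the shares at 5% and 8% rise to 52% and 28%.

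**Step 4: behaviour under a true excess.** By simulation, 40,000 trials per scenario:

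| Risk, loncastuximab tesirine vs idelalisib | At least one pause | First at 1 vs 0, of paused | Two or more further loncastuximab tesirine events with no new crossing, of paused |
|---|---|---|---|
| 3% vs 1% | 86% | 70% | 47% |
| 6% vs 3% | 90% | 31% | 68% |

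The rule therefore nearly always forces one evaluation when there is an excess. Under reading (b) it often forces no second one.

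**Step 5: what re-arming would buy and cost.** Under reading (c), a second pause occurs in 18% of trials at equal 1% against 67% at 3% vs 1%, and in 48% at equal 3% against 82% at 6% vs 3%. It does discriminate. The price is a mean of 0.8, 1.7 and 2.5 pauses per trial at equal risks of 1%, 3% and 5%, all of them due to chance.

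**Step 6: the readings against the text.** Enrolment is "study enrollment will be paused for safety evaluation if any of the following occur". The pause serves the evaluation, so it ends with the evaluation's outcome. Reading (a) would leave the evaluation without a function.

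**The case for a change.** The best case for a change is that a pre-specified rule should not depend on goodwill. The evaluator is the sponsor, the protocol text describes no independent data monitoring committee, and section 9.3 covers only futility on complete response. If enrolment resumes at 1 against 0, nothing written obliges anyone to pause at 2, 3 or 4 against 0. A few sentences would settle it, and step 5 shows that a re-armed rule separates a real excess from chance better than the first trigger alone.

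The textual part stands: no resume or re-trigger condition is given. Three things limit what follows from it.

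- **The silence is general.** It lies in the opening and closing sentences of section 4.3, so it applies to rules 2 and 3 as well. It is not a defect in how rule 1 is built.
- **A silent rule is not a blind sponsor.** Serious adverse events must reach the sponsor within 24 hours of the site learning of them (section 8.2). Investigators notify ethics committees as those committees require (section 10.1). The sponsor may terminate at any time (sections 5.5.2 and 10.7). These are not a formal re-trigger, but a second or third death after a completed evaluation would not go unseen.
- **The doubt about the count is small.** Table 7 ties Grade 5 to an adverse event, not to study drug, and section 8.4 says causality does not decide whether an event is reported. The word toxicity and the later restriction to related serious events leave some room, which the safety team can settle when it sets up the count.

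Re-arming is also a choice, not a correction. Whether up to 2.5 chance pauses per trial is a fair price depends on a Grade 5 rate the documents do not give, and on how the sponsor weighs delay against vigilance.

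**Conclusion.** No change to the plan follows. Rule 1 is met at 1 against 0, can be cleared only by an idelalisib Grade 5 event, and has no stated resume or re-trigger condition. At assumed equal risks of 1% to 8% it pauses 51% to 73% of trials, and 2% to 35% of those cross again. A first trigger this sensitive may well be intended, and it leads only to an evaluation.

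The stronger claim, that the rule is usually used up by the first event, does not hold generally. It is true up to about 3.5% equal risk with events known at enrolment, and false above that (32% at 5%, 11% at 8%).

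The harm arises only if the silent text is read in the least sensible way: that the pause outlasts its own evaluation, or that a sponsor that has just reviewed one death ignores the next. What remains is missing operational detail common to all three rules, and the one concrete remedy trades better discrimination for more chance pauses. Every percentage here rests on assumed Grade 5 risks; the reading of the text does not.
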